## STUDY DESIGN

Overview. In a 6-week pilot RCT, we will assess the feasibility and preliminary efficacy of an immersive mindfulness VR treatment (RelieVRx) versus a non-immersive sham VR control (sham VR) for the treatment of pain and OUD. We will recruit 40 adults with OUD and chronic pain enrolled in an MMTP and randomize 1:1 to RelieVRx vs sham VR. Over 6 weeks, participants in both groups will participate in 20-30 minute VR sessions twice per week at the MMTP. Over the course of the study, the research team will conduct pain and psychological assessments at baseline, 3 weeks, and at the study conclusion at 6 weeks. We will also explore changes in stress and inflammatory saliva and blood biomarkers at baseline, 3 weeks and 6 weeks. To assess feasibility, we will examine recruitment and retention and assess patient satisfaction. Our preliminary efficacy co-primary outcomes are (1) change in pain intensity and (2) change in opioid craving between treatment groups at 6 weeks. Secondary outcomes will include changes in pain interference, physical functioning, depression, anxiety, sleep quality, illicit opioid use, and prescription opioid use. In a separate aim, we will also explore changes in stress and inflammatory markers over the course of the trial.

Setting and Participants. We will recruit and conduct study visits at one Montefiore Opioid Treatment Program (OTP). Montefiore has the largest network of OTPs in New York State. Three of the five Montefiore OTPs comprise the Montefiore Division of Substance Abuse (DoSA) Wellness Centers; in total, these sites serve approximately 3,000 individuals. Electronic health data indicates that of 945 people with a chronic pain diagnosis who are on methadone for OUD, 555 (59%) are Male, mean age is 58.3, 566 (60%) are Hispanic, 170 (18%) are Black, and 140 (15%) are White.

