Participants: We will enroll 40 participants. As the narration of the VR device is only provided in English at this time, we require English proficiency for this pilot trial. Inclusion criteria: 1) ≥18 years old, 2) English proficiency; 3) receiving methadone treatment for DSM-5 confirmed OUD in the Montefiore network for at least 12 weeks, with no dose change in 14 days to ensure treatment stability; 4) chronic pain of at least moderate pain severity (score ≥4 on the Pain, Enjoyment of Life, and General Activity (PEG) scale); 5) willingness to participate in all study components; and 6) ability to provide informed consent, assessed using consent teach-back. Exclusion criteria: 1) conditions that could make participation in VR hazardous or cause adverse effects (current or prior diagnosis of epilepsy, seizure disorder, dementia, or migraines, any medical condition predisposing to nausea or dizziness, hypersensitivity to flashing light or motion), 2) conditions that could prevent proper use of the VR headset (stereoscopic vision or severe hearing impairment, or injury to eyes, face, or neck that prevents use of the VR headset), and 3) acute exacerbation of psychiatric conditions that preclude the ability to participate in the study. Pregnant patients are NOT excluded from the trial as there are no contraindications to their use of a VR device, but we are not specifically targeting pregnant patients for this study nor are we testing for pregnancy.

**Recruitment, Screening, and Randomization**. Recruitment will be active and passive in the OTP. Based on our team's prior DoSA trials and the scope of this current project, we anticipate enrolling 1-2

participants weekly. Research staff will enroll from one DoSA site for the duration of the trial; we will plan our recruitment strategy in conjunction with other IMPOWR-ME trials as to not recruit from the same pool of patients at a site at the same time. We expect retention of approximately 85% based on our groups prior DoSA trials.  **Screening:** After obtaining written consent, we will administer a screening questionnaire. Potentially eligible subjects will then complete a written informed consent process including discussion of procedures and risks and benefits before being randomized. Consent will occur in a private area of the OTP. **Randomization**: Randomization will occur using block randomization (blocks

of 4) to two conditions in a 1:1 ratio.

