**Data sources, measures, and management.** Study assessments will take place onsite at the OTP at weeks 0, 3, and 6 and last 30-60 minutes. Participants will receive \$50 compensation at each study assessment. We will track the number of patients screened, eligible, consented, and retained. During assessments, participants will answer surveys and submit saliva and blood. In addition, we will extract information from the Montefiore EMR, SMART EMR (methadone dosage), and from the New York State Prescription Monitoring Program (PMP). Study measures are listed in Table 1; where possible we align our measures with IMPOWR CDEs and with IMMPACT recommendations for study of chronic pain. All measures will be examined at each study visit, at 0, 3 and 6 weeks. All study assessment data will be managed in REDCAP, a well-established, HIPAA-compliant web-based surveying platform and database. During twice weekly VR sessions, we will also conduct before and after surveys to ask about experiences during VR exercises not taking more than 5 minutes; these will be paper based, scanned, and uploaded to Montefiore BOX, a HIPAA-compliant online cloud storage service. A portion of blood will also be bio-banked to facilitate future biomarker analyses. We will conduct an optional qualitative interview exploring experiences in the trial at the conclusion of the trial; participant interviews will be recorded and transcribed for analysis.

**Informed Consent.** The RA will screen all potential participants for inclusion and exclusion criteria in a private area of the MMTP. First, we will obtain written consent to administer a screening questionnaire. Screening questionnaire questions will focus on inclusion and exclusion criteria, pain history, and also ask about prior use of virtual reality devices. The initial screening questionnaire will take 15 minutes. Participants will not be reimbursed for the screening questionnaire. Written consent and the initial screening questionnaire will occur in a private area of the MMTP.

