Potentially eligible subjects will then complete a written informed consent process with HIPAA authorization including discussion of procedures and risks and benefits before being randomized. Consent will occur in a private area of the OTP. The RA will perform consent teach-back to assure that participants are aware of the details of the consent. Participants who give consent and are randomized will then complete the first study visit at a convenient time. Participants will be reimbursed \$50 for their participation at each study assessment. If they choose to participate in the optional qualitative component, they will be reimbursed an additional \$30.

Tests and procedures, including blood draws and saliva samples, performed at study assessments will not be billed to participants.

Patient privacy protection. We will strip patients' protected health information from all data before conducting analyses. As in prior studies we have conducted, we will have a "name-based" and an "ID-based" identification system that will remain separate. In the name-based system, all documents that have patient identifiers will be filed together. Some of these documents will have participants' signatures (e.g., consent forms). In the ID-based system, all documents that do not include identifying information or signatures will use participants' unique study IDs (rather than names) and will be filed together. All forms will contain either a "name-based" or an "ID-based" identifier, but never both. There will be only one electronic document that links participants' names to their study IDs; only the study staff will have access to this document, which will be password protected and kept on password-protected servers.

Study data will be kept in a password-protected, encrypted file on password-protected servers that are backed up daily. No one but the study team will have access to study data. Publication or presentation of study results will not include information that would allow for identification of providers or patients.

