**Analytic plan.** Feasibility: Feasibility outcomes will be measured as proportions. Preliminary Efficacy: To examine the association between treatment arm and the co-primary outcomes, we will use separate 2-level mixed-effects linear regression model with the treatment arm as a mixed effect with participant-specific random intercepts to account for hierarchical data. The difference in trends of pain intensity and opioid craving will be represented by the time-by-arm interaction. For secondary outcomes and stress and inflammation exploratory outcomes, we will use a similar strategy; where outcomes are dichotomous, we will use 2-level mixed effects logistic regression models.

We will use thematic analysis to analyze transcripts in the qualitative study.

**Power analysis**. The primary purpose of this study is to test feasibility and to generate preliminary data for a future R01 application. We are able to enroll 40 participants in the pilot RCT given our resources and given the time of this study. We base our conservative power analysis on t-tests of change in our pain intensity preliminary efficacy outcome and use effect size estimates from a study of RelieVRx. In that study, the pre-post difference in pain intensity was 2.2 in the treatment group and 1.2 in the control group. Given the effect size of d=0.49, and 20 participants in each arm, we will have 70% power to detect a difference of this magnitude or larger. We expect to have greater statistical power using mixed effects linear regression models with repeated measures over time.

**Risks/Benefits**. We expect the major risks to be associated with the VR technology. VR can sometimes cause "cybersickness" in some patients, especially when playing or experiencing fast moving games or videos. RelieVRx is a much less intense program designed to minimize these sensations. In the clinical trial of RelieVRx, about 10% of participants reported some nausea and/or motion sickness, but these symptoms were temporary and none decided to terminate their use of the technology because of adverse events. In our preliminary data of 20 patients, no patients have reported any issues with cybersickness. Nonetheless, this will be an important risk to discuss with patients.

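### The co-primary time-by-arm term is in effect a change-score contrast: valid, but less precise than an analysis that adjusts for the baseline already collected

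*Combined protocol and SAP*

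**What the plan says.** All places are in the combined protocol and SAP, under STUDY DESIGN.

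- **Overview.** The preliminary-efficacy co-primaries are "change in pain intensity and (2) change in opioid craving between treatment groups at 6 weeks".
- **Data sources, measures, and management.** "All measures will be examined at each study visit, at 0, 3 and 6 weeks". Week 0 is therefore one of three repeated outcome values.
- **Analytic plan.** Each co-primary has its own two-level linear model "with the treatment arm as a mixed effect with participant-specific random intercepts to account for hierarchical data". The effect is defined as follows: "The difference in trends of pain intensity and opioid craving will be represented by the time-by-arm interaction". The fixed effects are not listed, and the plan does not say whether time is linear or categorical. A baseline covariate or a common baseline mean is not mentioned. Secondary outcomes follow a similar strategy.
- **Informed Consent.** On the timing of week 0: "Participants who give consent and are randomized will then complete the first study visit at a convenient time".
- **Participants.** Entry requires a "score ≥4 on the Pain, Enjoyment of Life, and General Activity (PEG) scale".
- **Power analysis.** The calculation uses t-tests of change with d = 0.49 and 20 per arm and claims 70% power. It expects the mixed model to do better.

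**The concern.** Randomisation makes the true pre-treatment means equal in the two arms. A model with a free arm effect at week 0 ignores this. It spends information estimating a baseline difference known to be zero in expectation, and then subtracts the noisy estimate. The collected baseline serves only to form a change score.

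Precision is what this trial lacks. The sample is fixed at 40 by resources, and the stated aim is to supply estimates for a larger grant application. The plan also expects its mixed model to beat a t-test of change. With complete data, the model as naturally read has the same variance as that t-test, so almost none of the expected gain appears.

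The specification is also unclear. The wording "with the treatment arm as a mixed effect with participant-specific random intercepts" does not define a model: each participant has one arm, so arm has to be a fixed effect.

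**Working it through.** **Inputs from the documents.** 20 per arm; d = 0.49; visits at weeks 0, 3 and 6; random intercept only; about 85% retention, so about 17 per arm (3 of 20 lost). From the Power analysis: "the pre-post difference in pain intensity was 2.2 in the treatment group and 1.2 in the control group". The difference is 1.0, so the implied SD of change is 1.0/0.49 = 2.04.

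**Assumed, because not stated.** Two-sided alpha of 0.05; correlation rho between baseline and week 6 (range shown); equal SDs at weeks 0 and 6 unless varied below.

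**1. The plan's own figure.** A two-sample t-test with d = 0.49 and 20 per arm has 32.7% power (exact noncentral t, 38 df), not 70%. One-sided 0.05 gives 45.1%. About 52 per arm would be needed for 70%. This is a separate problem, but it sets the starting point here.

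**2. The planned contrast.** With outcome variance s² and complete data, the week-6 interaction with a free baseline has variance 2(1 − rho)s² × 2/n. This is the variance of the difference in mean change. In simulated complete data the two estimates agreed to about 1e-14. With linear time the variance is the same, because the visits are equally spaced.

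**3. Using the baseline.** Adjusting for week 0, or constraining both arms to one week-0 mean, gives (1 − rho²)s² × 2/n. The ratio is (1 − rho²)/[2(1 − rho)] = (1 + rho)/2, so the saving is (1 − rho)/2.

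| rho | variance ratio | saving, complete data | saving, 3 of 20 per arm lost after week 3 | power, 20 per arm (37 df) |
|---|---|---|---|---|
| 0.3 | 0.65 | 35% | 1 − 0.76/1.11 = 32% | 47% |
| 0.5 | 0.75 | 25% | 1 − 0.87/1.12 = 22% | 41% |
| 0.7 | 0.85 | 15% | 1 − 0.97/1.12 = 13% | 37% |
| 0.8 | 0.90 | 10% | 9% | 36% |
| 0.9 | 0.95 | 5% | 4% | 34% |

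The dropout column divides the constrained variance by the free-baseline variance, each relative to the complete-data change score. Power uses d/√ratio: at rho 0.3, 0.49/√0.65 = 0.61.

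**4. Unequal SDs.** With q = SD at week 0 / SD at week 6, the saving from covariate adjustment is 1 − (1 − rho²)/(1 + q² − 2·rho·q). At rho 0.3, 0.5 and 0.7:

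- q = 0.85: 25%, 14%, 4%
- q = 0.70: 15%, 5%, 0%
- q = 1.15: 44%, 36%, 28%

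The PEG entry floor is a reason to think q could be below 1 for pain.

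**5. Cost of estimating the slope.** With 40 participants, covariate adjustment inflates the variance by about 1 + 1/36 = 1.03. The ratio at rho 0.3 becomes 0.65 × 1.03 = 0.67. A simulation of 40,000 trials per setting gave 0.67, 0.77 and 0.87 at rho 0.3, 0.5 and 0.7. The real savings are therefore about two to three points below the complete-data column.

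**The case against.** The strongest defence is that the planned contrast is a standard, valid analysis that matches the stated outcome, change between groups at 6 weeks. That stands. A reader might infer that chance baseline imbalance biases the result. It does not: the contrast is unbiased under randomisation. The chance of an imbalance above half an SD (11% at 20 per arm) is the same sampling variability already counted in the variance ratio, not an added harm.

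Three further points stand in part.

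- **Size.** A reader might take 15-35% as a property of this trial. The documents support neither the correlation nor the equal SDs behind it, and plausible departures bring the saving close to zero. With complete data and a known slope it is never negative. After the cost of estimating the slope, the worst case is a loss of about 3%.
- **Specification.** A free baseline is the natural reading, not a stated one, since the fixed effects are not listed. The mixed-effect wording may be a slip. Either way the text needs completing. Exact equality with the change score also fails once data are missing, although the precision gap remains.
- **Timing.** Week 0 follows randomisation. Equal true means at week 0, or a sound covariate, require that allocation could not have influenced the answers. The plan does not say so. The screening PEG is a tempting substitute but a poor main remedy. It does not cover craving, and it is not the baseline of PROMIS Pain Intensity, which Table 1 also lists for pain. If its correlation with the week-6 outcome is r, the ratio to the planned contrast is (1 − r²)/[2(1 − rho)]. At rho = 0.7 this exceeds 1 whenever r² < 0.4, that is r below about 0.63, so it could be less precise than the plan.

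**Conclusion.** The point holds as one of efficiency and incomplete specification, not of validity. As naturally read, the co-primary analysis is a change-score contrast and gives up precision that the collected week-0 values could supply. Under assumed correlations of 0.3 to 0.7 and equal SDs, the variance saving is about 35% to 15%, or 32% to 13% with the expected loss placed after week 3. It is about 10% to 5% at correlations of 0.8 to 0.9, and less if the baseline SD is narrowed.

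A reader might infer that the change would restore the stated power. It would not: even at correlation 0.3, power at d = 0.49 is about 47%, against 33% as planned and 70% as stated. The change is still worth making before analysis, because the sample cannot be enlarged and the gain needs no new data.

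**What to change.** In the Analytic plan, for both co-primaries and the continuous secondary outcomes:

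1. List the fixed effects, with arm as a fixed effect and time as categorical.
2. Either model weeks 3 and 6 with the week-0 value of the same outcome as a covariate, or keep week 0 as an outcome and constrain both arms to a common week-0 mean. Name one of the two.
3. Name the week-6 arm contrast as the primary estimate.
4. State that week-0 pain and craving are recorded before the first VR session and before allocation is disclosed to the participant. If that cannot be assured, the adjustment loses its justification, and the plan should say so.

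The cost is small: one degree of freedom, about 3% of variance for estimating the slope, and a sentence in the plan, plus the statement on the timing of week 0. No new data are needed.

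### The co-primaries are changes at 6 weeks, but the model tests a difference in trends with no week-6 contrast; a plateau by week 3 would distort the standard error and, with dropout, shift the estimate

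*Combined protocol and SAP*

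**What the plan says.** All references are to the STUDY DESIGN part of the combined protocol and SAP.

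- **Outcome (Overview):** "Our preliminary efficacy co-primary outcomes are (1) change in pain intensity and (2) change in opioid craving between treatment groups at 6 weeks".
- **Model (Analytic plan):** a separate two-level linear mixed model for each co-primary, "with the treatment arm as a mixed effect with participant-specific random intercepts to account for hierarchical data". The tested term is described thus: "The difference in trends of pain intensity and opioid craving will be represented by the time-by-arm interaction".
- **Visits (Data sources, measures, and management):** "All measures will be examined at each study visit, at 0, 3 and 6 weeks".
- **Planning figures (Power analysis):** "the pre-post difference in pain intensity was 2.2 in the treatment group and 1.2 in the control group", followed by "Given the effect size of d=0.49, and 20 participants in each arm, we will have 70% power". The authors expect the mixed model to do better than the t-test behind that figure.
- **Retention (Recruitment, Screening, and Randomization):** about 85%.

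The plan does not say whether time is continuous or categorical. It names no contrast at week 6, and it specifies no within-participant covariance beyond the random intercept.

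**The concern.** The outcome is defined at one time point, while the tested term describes a course over three. A trend carried by a single interaction suggests a straight line. With three visits, a straight line leaves one departure per arm unmodelled: how far the week-3 mean lies from the midpoint of weeks 0 and 6. If participants improve early and then level off, two things follow.

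- The week-3 departure is counted as residual error, so the standard error of the co-primary contrast no longer reflects its true sampling variation.
- Participants who leave after week 3 contribute the steep early segment to the slope. The extrapolated 6-week difference then moves away from the difference the Overview defines.

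At stake are the interval and test for both co-primaries, and the variance and effect estimates that the pilot is meant to supply for a later grant application.

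**Working it through.** **Inputs from the plan:** mean improvement in pain intensity 2.2 and 1.2, difference 1.0; d = 0.49; 20 per arm; visits at 0, 3 and 6 weeks; retention 85%.

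**Assumptions:** d is scaled by the SD of change, so SD = 1.0/0.49 = 2.04 (range 1.5 to 3.0 also shown); two-sided 5% test; dropouts miss week 6 only, at random.

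**1. The plan's own figure.** A two-sample t-test with d = 0.49 and 20 per arm has 33% power, not the stated 70%. That is a separate and larger matter. Below, 33% is the reference.

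**2. Point estimate, complete data.** With equally spaced visits the least-squares slope is (week 6 − week 0)/6, so 6 × slope equals the 6-week change exactly. Simulated means were −0.99 in both the linear and the categorical model (true −1.0).

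**3. Standard error, complete data, random intercept correct.**
- Residual variance: 2.04²/2 = 2.08.
- True SE of the difference in change: √(2 × 2.04²/20) = 0.645.
- Quadratic contrast (1, −2, 1) under a full plateau at week 3: arm means of size 2.2 and 1.2.
- Its sum of squares: 20 × (2.2² + 1.2²)/6 = 20.9.
- Pooled over 80 − 2 = 78 within-participant degrees of freedom: 20.9/78 = 0.268.
- Relative increase in residual variance: 0.268/2.08 = 12.9%.
- Model SE: 0.645 × √1.129 = 0.686, an excess of about 6%.

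A REML simulation (1,500 trials) gave a mean SE of 0.683 for linear time and 0.642 for categorical time, against an empirical SD of 0.635. Power falls from about 33% to 29%, and type I error is a little under 4%.

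| Week-3 share of the 6-week change | Variance added | SE excess |
|---|---|---|
| 50% (linear course) | 0 | 0 |
| 75% | 3.2% | 1.6% |
| 100% (full plateau) | 12.9% | 6.2% |

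For the full plateau, an SD of 1.5 gives 0.268/1.125 = 23.9% more variance (SE excess 11%). An SD of 3.0 gives 0.268/4.5 = 6.0% (SE excess 3%).

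**4. Estimate with 15% dropout.** Take 3 of 20 per arm missing week 6, with intercept variance equal to residual variance (assumed). For an arm with mean course (0, 1, 1), the generalised least-squares slope is 825/4770, so 6 × slope = 1.038 rather than 1.
- Both arms plateau: 1.038 × 2.2 − 1.038 × 1.2 = 1.04, a drift of about 4%.
- Only the treated arm plateaus, control linear: 1.038 × 2.2 − 1.2 = 1.08, a drift of about 8%.

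Simulation gave 1.045 and 1.068 in size, with simulation error of about 0.02. The categorical model gave 1.003 and 0.979.

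**5. If correlation decays between visits.** Keep the SD of change at 2.04 and let the three visits follow AR(1) with adjacent correlation ρ. The quadratic contrast then has (3 − ρ)/(3(1 + ρ)) of the linear contrast's variance: 0.556 at ρ = 0.5 and 0.368 at ρ = 0.9. Under a full plateau, model SE divided by true SE is:
- linear time: √((38 + 40 × 0.556)/78 + 0.129) = 0.95 at ρ = 0.5, and 0.90 at ρ = 0.9;
- categorical time, random intercept kept: √((1 + 0.556)/2) = 0.88 at ρ = 0.5, and 0.83 at ρ = 0.9.

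Type I error is then about 6% to 8% for linear time, and about 8% to just over 10% for categorical time with the random intercept alone.

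**The case against.** The strongest case against acting has four parts.

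- **The straight line is inferred.** This stands: the plan never says that time is continuous. But the need for a fix does not depend on it. If time is categorical, the unspecified interaction has two degrees of freedom and is not the 6-week contrast either. On the same inputs and a linear course, the joint test has 25.5% power, against about 33% for the week-6 contrast.
- **The mismatch is largely nominal.** With complete data this is correct, as step 2 shows. A reader might infer that the trend model estimates the wrong quantity outright; the equally spaced visits rule that out unless week-6 data are missing. The plan itself expects about 15% loss.
- **The effect is small, and conservative where it applies.** This stands for the standard error. At a 75% week-3 share it is negligible, and even a full plateau costs about 4 points of power in a pilot whose main purpose is feasibility.
- **The direction is not established.** This also stands. A reader might infer that the intervals for both co-primaries are simply too wide. That holds only if the random-intercept covariance is about right. Under a full plateau the sign reverses once the adjacent-visit correlation in step 5 exceeds about 0.23. The documents give no correlation, and no figures at all for craving.

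The last point also limits the remedy. Categorical time with the random intercept alone would make false positives more frequent under decaying correlation, so the covariance has to change with it.

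**Conclusion.** The point holds in a limited form. The quantity tested is not specified as the quantity defined, and under a plausible early-plateau course the difference matters modestly. For pain intensity, a full plateau by week 3 makes the standard error about 6% too large (3% to 11% for SD 3.0 to 1.5) and takes power from about 33% to 29%. With 15% missing at week 6, the same plateau shifts the estimate by about 4% to 8%. With a linear course there is no loss.

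These sizes rest on linear time, an SD of change back-calculated from d, dropout at random after week 3 and, for the standard error, a correct random-intercept covariance. The trajectory is not in the documents, so the figures are a range. The documents do not support a general claim that the standard error is too large, nor any number for craving. The point deserves a change because the remedy is short and nearly free, not because the distortion is large.

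**What to change.** In the Analytic plan, for both co-primary models:

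- enter visit (weeks 0, 3, 6) as a categorical factor with its interaction with arm;
- use an unstructured within-participant covariance over the three visits in place of the random intercept alone, with small-sample degrees of freedom (for example Kenward–Roger);
- name the arm contrast in change from baseline to week 6 as the co-primary estimate, and report the week-3 contrast descriptively;
- remove the reference to a difference in trends.

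**Cost:** one or two sentences, two more mean parameters (6 instead of 4) and four more covariance parameters (6 instead of 2). With complete data the week-6 contrast then reduces to the two-sample comparison of change on 38 degrees of freedom. That has about 33% power, practically the same as the linear model when the course is linear, and it holds type I error near 5%. With 3 of 20 per arm missing week 6, and compound symmetry holding, the SE is 0.682 with categorical visit against 0.681 with linear time.

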Another risk is breach of confidentiality of patient data. Such a breach is unlikely, because all study staff will be trained in confidentiality and secure data management, and the data collected as part of this study will be stripped of protected health information.

In the major clinical trials of RelieVRx, both intervention and sham VR groups had reduced pain at the end of the trial, with the magnitude being larger in the intervention arm. However, this trial is shorter and some of the parameters are not the same, including the number of weeks of the intervention. Therefore, it is possible, but not certain, participants will receive a direct benefit.

**Data Safety Monitoring Plan**. Monitoring of recruitment and retention, adverse events, protocol deviations, and protocol violations will be ongoing by the Principal Investigator. Additionally, the PI and co-investigators will meet every 2 months in person to discuss recruitment, retention, data quality, and any adverse events. Together, they will make corrective plans as necessary. No interim analyses are planned for this pilot trial.

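### The stated 70% power does not follow from d = 0.49 with 20 per arm: the named t-test has about 33% power at two-sided 5% (45% one-sided), and about 28% at the plan's own 85% retention

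*Combined protocol and SAP*

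**What the plan says.** The Power analysis paragraph (STUDY DESIGN) names the test: "We base our conservative power analysis on t-tests of change in our pain intensity preliminary efficacy outcome". The effect comes from an earlier trial of the same device, in which "the pre-post difference in pain intensity was 2.2 in the treatment group and 1.2 in the control group". The paragraph then concludes: "Given the effect size of d=0.49, and 20 participants in each arm, we will have 70% power to detect a difference of this magnitude". It gives no alpha, sidedness, standard deviation or baseline-to-follow-up correlation. It adds that the repeated-measures mixed model should have more power than the t-test. It also says that the main purpose is feasibility and that 40 participants is what resources and time allow.

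Two other places bear on the figure:

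- Recruitment, Screening, and Randomization: "We expect retention of approximately 85% based on our groups prior DoSA trials".
- Risks/Benefits, comparing this study with the earlier trials of the device: "this trial is shorter and some of the parameters are not the same, including the number of weeks of the intervention".

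**The concern.** The paragraph supplies a test, an effect size, a per-arm sample size and a result, so the result can be checked directly. An effect of about half a standard deviation with 20 per arm is well known to give low power, and 70% looked about twice too high.

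The number matters even in a pilot. Change in pain intensity is a co-primary efficacy outcome, to be tested through a time-by-arm interaction. Someone who believes the 70% would take a non-significant result as fair evidence against the assumed effect. The same paragraph says that the data are meant to support a later R01 application, so the wrong figure could be carried forward.

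**Working it through.** **Inputs**

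- d = 0.49 and 20 per arm (Power analysis).
- Raw difference 2.2 − 1.2 = 1.0 point (Power analysis). If d is this difference divided by the SD of change, SD = 1.0 / 0.49 = 2.04 points. The plan gives no SD.
- Retention 85% (Recruitment, Screening, and Randomization): 0.85 × 20 = 17 per arm.
- Alpha is not stated. I assume 5% and show both one-sided and two-sided results.

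**Formula.** For a two-sample t-test with n per arm, df = 2n − 2 and the noncentrality parameter is d × √(n/2). Power is the probability that a noncentral t variable with these parameters falls beyond the critical value.

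**Attempt to reproduce 70%.** With n = 20, df = 38 and the noncentrality is 0.49 × √10 = 1.55.

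| Alpha, 20 per arm | Power |
|---|---|
| two-sided 0.05 | 32.7% |
| one-sided 0.05 | 45.1% |
| one-sided 0.10 | 59.9% |
| two-sided 0.20 | 60.2% |
| two-sided, about 0.30 | 70% |

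The normal approximation gives 34.1% at two-sided 0.05, so the choice of formula is not the cause.

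**With 85% retention.** For n = 17, df = 32 and the noncentrality is 0.49 × √8.5 = 1.43. Power is 28.3% two-sided and 40.3% one-sided at 5%.

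**What 70% would need (two-sided 5%)**

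- With 20 per arm: d = 0.81, or 0.81 × 2.04 ≈ 1.6 points. One-sided, d = 0.70.
- With 17 per arm: d = 0.88, or about 1.8 points.
- With d = 0.49: 53 completers per arm, 106 in total, and 106 / 0.85 ≈ 125 enrolled.

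**Where 70% might come from.** Each route found departs from the stated inputs:

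- 40 per arm, one-sided 5%: noncentrality 0.49 × √20 = 2.19, power 70.1%. This would mean that the total of 40 was entered as the per-arm number.
- A one-sample test within one arm of 20, one-sided 5%: 68.0% (t) or 70.8% (normal). This is not a comparison between arms.
- d standardised to a raw-score SD, with a baseline-to-follow-up correlation of about 0.82 (change score) or 0.79 (ANCOVA). The plan states no correlation.

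The first is the closest exact match, but the documents cannot show which of these occurred, if any.

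**Precision.** With SD of change 2.04, the 95% confidence interval half-width for the difference in mean change is t × 2.04 × √(2/n):

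- n = 20: 2.02 × 2.04 × 0.316 ≈ 1.31 points.
- n = 17: 2.04 × 2.04 × 0.343 ≈ 1.43 points.

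Both exceed the assumed difference of 1.0 point.

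**The case against.** The strongest reply is that this is a feasibility pilot. The sample size was set by resources, efficacy is labelled preliminary, and 70% did not determine the design. That is true and limits the practical weight, but it does not make the number right.

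A second reply is that the mixed model will do better. The plan attributes 70% to the t-test and treats the mixed model as a gain on top, so 70% is presented as a floor. The gain is also likely to be small. With visits at weeks 0, 3 and 6, complete data and time entered as a linear trend, each participant's slope is (−3·y0 + 0·y3 + 3·y6) / 18 = (y6 − y0) / 6. The interaction therefore estimates the same contrast as the change score. If the correlation between visits is constant, the extra degrees of freedom cannot lift power beyond the normal-theory 34.1%.

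Several narrower points stand in part:

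- The 33% and 28% assume two-sided 5%. One-sided, they are 45% and 40%, and the chance of missing the effect is about 55% instead of two in three.
- The SD of 2.04 assumes that d was standardised by the SD of change. If 2.04 is a raw-score SD, power at 20 per arm (two-sided 5%) is about 25%, 33%, 50% and 67% for correlations of 0.3, 0.5, 0.7 and 0.8. The half-widths become about 1.5, 1.3, 1.0 and 0.8 points.
- Seventeen per arm is a completers-only case. The mixed model can still use earlier visits from participants who leave.
- The word conservative may refer only to choosing a t-test over a mixed model.

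**Conclusion.** The concern holds. With the test, effect size and sample size that the plan states, power is 33% at two-sided 5% and 45% at one-sided 5%, against a stated 70%. At 17 per arm it is 28% and 40%. The alpha level is an assumption, but no conventional choice recovers 70%.

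The calculation is not conservative on any reading. It overstates the power of the t-test itself and makes no allowance for the expected dropout. It also takes d from an 8-week trial that the plan itself says differs from this 6-week study. The explanation that the total was used as the per-arm number is plausible but unconfirmed, and the conclusion does not depend on it. The figures in points rest on reading 2.04 as the SD of change.

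**What to change.** Replace the power sentences with wording such as:

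> The sample size of 40 is set by feasibility. With 20 per arm (17 expected at week 6) and two-sided alpha 0.05, a t-test of change has about 33% (28%) power for d = 0.49; 70% power is reached only for d of about 0.81 (0.88). Assuming an SD of change of 2.04 points, the 95% confidence interval for the difference in change will extend about 1.3 (1.4) points either side of the estimate. A non-significant result will not be taken as evidence of no effect.

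Remove the description of the calculation as conservative. State how d was standardised. If it was not by the SD of change, recompute the power and interval widths with a stated correlation. If the authors intended one-sided testing, say so and give 45% (40%).

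The cost is one paragraph of protocol wording. Sample size, procedures and analysis are unchanged. The stated power becomes less favourable.
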